#### IQVIA Belgium Longitudinal Patient Data (IQVIA LPD), Germany

Belgium Longitudinal patient data (LPD) is collected from GP prescribing systems and contains patient records on all signs and symptoms, diagnoses and prescribed medications. The information recorded allows patients and doctors to be monitored longitudinally. Data are recorded directly in the LPD from doctors' surgeries in real-time during patient consultations via a practice management software system. It is used in studies to provide various market insights such as treatment trends, patient pathway analysis and treatment compliance. The panel of contributing physicians (a stable 300 GPs) is maintained as a representative sample of the primary care physician population in Belgium according to three criteria known to influence prescribing: age, sex and geographical distribution. Currently, the database is covering 1.1 M cumulative patients and covers from 2012 through to the present. The panel consists of a stable 300 GPs that are geographically well spread. The total number of active GPs in Belgium is 15.602. The regional geographical spread of physicians in the LPD data is also representative of the distribution across the country: 57% GPs in the North (compared to 54% nationally), 31% in the South (33% nationally) and 12% in Brussels (13%). The provider of the data has more than 2.250 GPs under contract so in case of a drop out a replacement is easily found. Drugs obtained over the counter by the patient outside the prescription system are not reported. No explicit registration or approval is necessary for drug utilisation studies.

## Croatian National Public Health Information System (NAJS), Croatia

The National Public Health Information System (Nacionalni javnozdravstveni informacijski sustav - NAJS) is an organised system of information services by Croatian Institute of Public Health (CIPH). NAJS enables data collecting, processing, recording, managing and storing of health-related data from health care providers as well as production and management of health information. NAJS contains medical and public health data collected and stored in health registries and other health data collections including cancer registry, mortality, work injuries, occupational diseases, communicable and non-communicable diseases, health events, disabilities, psychosis and suicide, diabetes, drug abuse and others.

## 8.3 Study period

From 1st of January 2010 to end of data availability. For some databases the start date will be defined later (see "11. Limitations" for further details).

Authors: [name], [name], [name], [name], [name]

Version: V4.0

Dissemination level: Public

## 8.4 Follow-up

For the population-level DUS (objective 1), study participants in the denominator population will start contributing person time on the latest of the following: 1) study start date (1st January 2010, or as defined according to the database), 2) date on which they turn 10 years old, 3) date at which they have a year of prior history recorded. Participants will stop contributing person time at the earliest date of the following: 1) end of available data in each of the data sources, 2) date at which their observation period ends (e.g. loss to follow-up, death).

For the patient-level DUS (objective 2 to 5), participants will be followed up from the day of incident prescription of medication (index date), until the earliest end of data availability, date at which their observation period ends (e.g. loss to follow-up, death), or 180 days after ending treatment (objective 5). For objective 2, 4 and 5, index date will be defined as the date of the first-ever prescription of NOMAC or CMA. For objective 3, this will be defined as the date of the first-ever prescription of any of the 6 drug classes of interest (see "8.6.2 Outcomes").

For objective 4, line of treatment will be assessed retrospectively by looking at prior records of alternative treatments, from the date of initiation of treatment with products containing NOMAC or CMA to start of the study period (1st January 2010, or as defined according to the database).

For objective 6, follow-up will be the same as that for objective 1.

Information on the operational definition of index date is described in **Table 4**. Please note that, for objectives 1 and 6, each drug class of interest will be assessed separately, with the washout window specific to the drug class being studied (e.g., when studying NOMAC, the washout window will be applied with respect to this substance only). For objective 3, the washout will be applied to all the drug classes of interest combined.

Authors: [name], [name], [name], [name], [name]

Version: V4.0

**Dissemination level:** Public

Table 4. Operational definition of time 0 (index date) and other primary time anchors.

Study population names	Time Anchor Description (e.g. time 0) 	Number of entries 	Type of entry	Washout window	Care Setting 	Code Type 	Incident with respect to
General population (objective 1 and 6)	Study entry date	Multiple entry	Incident , prevale nt	[-365, -1]	IP, OP	N/A	Outcome drug class (assessed separately)
Patients with prior history of meningioma (objective 1, subgroup analysis)	Date of diagnosis	Single entry	Incident	[-Inf, 0]	IP, OP	SNOME D	Meningiom a
New users of NOMAC (objective 2, 4 and 5)	Date of prescription	Single entry	Incident	[-Inf, -1]	IP, OP	RxNorm	NOMAC
New users of CMA (objective 2, 4 and 5)	Date of prescription	Single entry	Incident	[-Inf, -1]	IP, OP	RxNorm	СМА
New users of drug classes or progestogens of interest (objective 3)	Date of prescription	Single entry	Incident	[-Inf, -1]	IP, OP	RxNorm , SNOME D	Drug classes of interest (any)

¹ Study entry date (objective 1 and 6) will be defined as the latest of the following: 1) study start date (1st January 2010, or as defined according to the database), 2) date on which they turn 10 years old, 3) date at which they have a year of prior history recorded.

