#### **Exposures**

- Objective 1: N/A
- Objective 2, 4 and 5: First-ever prescription of NOMAC or CMA (assessed separately)
- Objective 3: First-ever prescription of NOMAC or CMA (assessed separately)
- Objective 6: N/A

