In July 2022, PRAC issued further recommendations for both NOMAC and CMA. PRAC recommended to update the summary of product characteristics for products containing NOMAC or CMA to inform of the risk of meningioma. PRAC recommended that medicines containing high-dose chlormadinone (5 – 10 mg) or high-dose NOMAC (3.75 – 5 mg) should be used at the lowest effective dose and for the shortest duration possible. These medications should only be used when other interventions are not appropriate and should no longer be considered for first-line treatment. Similar to what was already established for NOMAC, treatment with products containing NOMAC or CMA was contraindicated in patients with current or prior history of meningioma. PRAC also recommended monitoring patients for symptoms, and permanently discontinuing treatment if the patients develop meningioma. (9) Measures recommended by PRAC were endorsed by the Committee for Medicinal Products for Human Use (CHMP) and the European Commission issued final legally binding decisions applicable in all the European Union (EU) Member States, between 28th of October and 28th November 2022.(10) Following this decision, a direct healthcare professional communication (DHPC) was sent to prescribers (8th November 2022)(11) and Marketing Authorisation Holders (MAH) had one month to implement changes (28th December 2022). Dates for national-level interventions varied, especially in the case of France, where additional interventions were put in place between 2018 and 2021.

The overall aim of the study is to describe how prescribing of NOMAC and CMA has changed following the introduction of risk minimisation measures (RMM) in November 2022. To contextualise findings, it is also of interest to study changes in prescribing of other relevant drug classes, including progestogen and oestrogen combination products and progestogens that are pregnadien derivatives, and to study the impact of prior EU-level restrictions in trends of NOMAC prescribing.

D2 C	2 000	Charles	Donate and
P3-C.	3-UU6	Stuav	Protocol

Version: V4.0

**Dissemination level:** Public

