#### Other comorbidities:

- Hyperlipidaemia
- Hypertensive disorder
- Osteoporosis
- Neoplasm of the brain
- Neoplasm of the breast
- Cancer (any malignancy)
- Venous thromboembolism

Pre-specified concomitant medications will consist of the drug classes of interest included in this study.

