#### **Medications of interest:**

#### Drug classes of interest:

- Progestogen and oestrogen combination products not including NOMAC or CMA.
- Progestogens that are pregnadien derivates not including NOMAC or CMA.
- NOMAC (high- and low-dose products, assessed separately)
- CMA (high- and low-dose products, assessed separately)
- Medroxyprogesterone

Drugs used in the management of conditions for which medications of interest might be prescribed:

- Antidepressants
- Antihyperglycemics (Metformin)
- Bisphosphonates
- Clonidine
- Gonadotropin Releasing Hormone antagonists
- Anti-androgens (bicalutamide, flutamide, finasteride, spirolactone, cyproterone acetate)

A preliminary list of concepts to identify pre-specified comorbidities and comedications is detailed in the **Appendix I**. Comorbidities will be measured for any time prior to 1 day before index date, 365 days prior to 1 day before index date and at index date. Concomitant medications will be described 365 days prior to 31 days before index date, and 30 days to 1 day before index date, and at index date.

The operational definition of the covariates is described in the Table 9.

Authors: [name], [name], [name], [name], [name]

Version: V4.0

Dissemination level: Public

**Table 9.** Operational definitions of covariates.

Characteristic	Details	Type of variable	Assessment window	Care Setti ngs 	Code Type	Diagn osis Positi on 	Applied to study populations
Age groups	Defined as: 10-17, 18-34, 35-49, 50-64, +65.	Categorical	N/A	IP, OP	N/A	N/A	General population (objective 1 and 6)
Dose (NOMAC and CMA)	High vs. low doses. For NOMAC, high doses will include amounts from 3.75mg to 5mg. For CMA, high doses will include amounts from 5mg to 10mg. Low doses will be any amounts less than those specified.	Categorical	0	IP, OP	N/A	N/A	General population (objective 1 and 6)
Indication	Non-HRT vs. HRT. Age will be used as a proxy (non-HRT in women aged 10-49 years, HRT in women aged >50 years).	Categorical	0	IP, OP	N/A	N/A	General population (objective 1 and 6)
Comorbidities	Large-scale characterisation and pre-specified conditions 	Binary	[-Inf, -1], [- 365,-1], 0	IP, OP	SNO MED	Any	New users of drug classes or progestogens of interest (objective 3)

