#### A. Primary analysis

Hypothesis:	Objective 1: Not applicable, descriptive analysis.
	Objective 2: Cumulative dose and duration of treatments with NOMAC or CMA will be lower after the implementation of restrictions.
	Objective 3: The number of new users of NOMAC or CMA with prior history of meningioma will be reduced after the implementation of restrictions.
	Objective 4: The number of users initiating NOMAC or CMA as first-line treatment will be reduced after the implementation of restrictions.
	Objective 5: The number of discontinuations and switches from NOMAC or CMA to other drug classes will increase after the implementation of restrictions.
	Objective 6: The incidence of NOMAC or CMA will be reduced after the implementation of restrictions, especially for high-dose products. This reduction will not be observed for other drug classes of interest.
Exposure contrast:	Objective 1: Not applicable, descriptive analysis.
	Objective 2: Pre-intervention (1-year period) vs. Post-intervention (1-year period)
	Objective 3 to 6: Pre-intervention vs. Post-intervention
Outcome:	Objective 1: Incidence rates and prevalence of drug classes of interest
	Objective 2: Cumulative dose and treatment duration of NOMAC or CMA.

Authors: [name], [name], [name], [name], [name]

Version: V4.0

Dissemination level: Public

	Objective 3: Number and characteristics of users of drug classes of interest.
	Objective 4: Line of treatment when initiating NOMAC or CMA.
	Objective 5: Diagnosis with meningioma during treatment. Discontinuations and switches
	from treatments with NOMAC or CMA to others.
	Objective 6: Incidence rates of NOMAC or CMA.
	Drug classes of interest, NOMAC and CMA will be assessed separately.
Analytic software:	R
Model(s):	Objective 1: Not applicable, descriptive analysis.
	Objective 2 to 5: Standardised mean differences.
	Objective 6: Segmented regression (Poisson models).
Confounding adjustment method	
	Stratification.
Missing data methods	
	The absence of a record for a condition or medication will be considered as the absence of the disease or use of the medication.
Subgroup Analyses	
	Objective 1: Age groups, indication, study period. For NOMAC or CMA only: dose, WHO ATC 5 th level (if counts allow). A subgroup analysis will be performed restricting the study population to individuals with a prior history of meningioma.
	Objective 2: Study population, indication, study period.
	Objective 3: Study period.

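### Objective 3's combined lifetime washout leaves out NOMAC or CMA starts that follow another study class, although its hypothesis and dose counts are worded for new NOMAC/CMA users in general

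*Protocol*

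**What the plan says.** Protocol section 8.4 sets the Objective 3 index date: "For objective 3, this will be defined as the date of the first-ever prescription of any of the 6 drug classes of interest". It adds: "For objective 3, the washout will be applied to all the drug classes of interest combined". The Table 4 row "New users of drug classes or progestogens of interest (objective 3") specifies single entry, incident use and a washout of [-Inf, -1] with respect to any class. Table 6 excludes anyone with an earlier prescription of any class over the same window, and Table 7 defines the exposure in the same way.

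The Objective 3 hypothesis in Table 11 reads: "The number of new users of NOMAC or CMA with prior history of meningioma will be reduced after the implementation of restrictions". Table 1 words it as fewer new NOMAC/CMA users. Section 8.8 also plans to report how many patients start high- or low-dose NOMAC and CMA.

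On comedication, section 8.6.3 says: "Pre-specified concomitant medications will consist of the drug classes of interest included in this study". It then lists further drugs (antidepressants, metformin, bisphosphonates and others). The windows are: "Concomitant medications will be described 365 days prior to 31 days before index date, and 30 days to 1 day before index date", plus the index date itself.

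The abstract's list of exposures differs from all of this: "Objective 3: First-ever prescription of NOMAC or CMA (assessed separately"). Section 6 reports that, under the 2022 measures, high-dose products "should no longer be considered for first-line treatment".

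**The concern.** The cohort rule and the question do not match. A woman who used another combination product or pregnadien derivative and later starts NOMAC or CMA is a new NOMAC/CMA user in Objectives 2, 4 and 5. In Objective 3 she can enter only at her earlier product, if eligible then, and her NOMAC or CMA start is never described.

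The size of the omitted group depends on the intervention. If prescribers respond to the 2022 measures by trying another study class first, more high-dose starts become non-first and drop out of Objective 3 after the intervention. Both the count of new users and the count with prior meningioma can then fall without any fall in prescribing. Separately, some pre-specified rows cannot carry information, and the abstract and Appendix I point to different cohorts.

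**Working it through.** The plan gives no figure on this point, so the check sets the rules side by side and then illustrates the size.

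**1. Entry rule against line of treatment.** Objective 4 (section 8.8) calls a NOMAC/CMA start non-first when there is an earlier record of a study class not containing NOMAC or CMA. Objective 3 requires no earlier record of any study class. Every Objective 4 non-first start therefore fails the Objective 3 rule. The loss is wider than that: NOMAC after CMA and CMA after NOMAC also fail, although Objective 4 does not count them as non-first. Hence

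share lost from Objective 3 (L) ≥ non-first share in Objective 4.

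**2. Check on invented histories.** Both rules were applied to 200,000 made-up prescription histories, once with the Table 7 wording (classes plus progestogens) and once with the Appendix I code list. The product mix is arbitrary, so only zero against non-zero, and the direction of the inequality, carry meaning.

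| | Table 7 wording | Appendix I list |
|---|---|---|
| First-ever NOMAC users | 89,484 | 89,484 |
| Non-first under Objective 4 | 24,461 | 24,461 |
| Kept in Objective 3 as NOMAC starters | 44,732 | 53,440 |
| Non-first among those kept | 0 | 0 |
| Lost | 89,484 − 44,732 = 44,752 | 89,484 − 53,440 = 36,044 |

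In both columns the number lost exceeds 24,461, as step 1 implies.

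**3. Look-back rows.** For the study's own classes, [-365, -31] and [-30, -1] lie inside [-Inf, -1], so the washout empties them. The exception is medroxyprogesterone. Table 7 includes it in the washout as a progestogen of interest. The Objective 3 row of Appendix I lists only G03AA, G03AB, G03DB, G03FA and G03FB, which leaves out G03AC06 and G03DA02. In the invented histories all study-class rows were zero under Table 7. Under Appendix I, only those two codes had earlier records (5,022 and 5,025).

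**4. Size of the artefact.** Let N be the number of NOMAC/CMA initiators in a period. Objective 3 sees N(1 − L). With N equal in both periods,

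change in visible count = (1 − L_post)/(1 − L_pre) − 1.

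Taking L_pre = 30% as an assumption:

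| L_post (assumed) | Visible per 100, pre → post | Change |
|---|---|---|
| 30% | 70 → 70 | 0% |
| 40% | 70 → 60 | 60/70 − 1 = −14% |
| 50% | 70 → 50 | 50/70 − 1 = −29% |
| 60% | 70 → 40 | 40/70 − 1 = −43% |

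If a fraction m of initiators has prior meningioma whatever the line of treatment, the visible count N(1 − L)m falls by the same factor while the proportion stays at m. If m differs by line, Objective 3 estimates it only among starters naive to all study classes.

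**5. Separate reporting does not repair this.** Section 8.6.3 lists time period as the only stratifier for Objective 3, while Table 11 has a general line that the classes, NOMAC and CMA are assessed separately. Even if the cohort is split by the product started, its NOMAC and CMA parts hold only women with no earlier study-class use.

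**The case against.** The combined washout is deliberate. Section 8.4 contrasts it with the substance-specific washout of Objectives 1 and 6, section 7 says Objective 3 covers all relevant classes, and a cohort of first-time users of any study class is a coherent descriptive population. This stands, and it is why that cohort should be kept. It does not make the cohort suit a hypothesis about new NOMAC/CMA users.

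A reader might infer several stronger things that the protocol does not support:

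- That all prior-medication windows are empty. The other listed comedications and the large-scale characterisation of other codes are untouched, and the day-0 window shows which product was started.
- That women with earlier use are removed altogether. They can enter at their first study class; their later NOMAC or CMA start is what is lost.
- That contraindicated use in second-line users goes unseen. Objective 1's meningioma subgroup covers NOMAC and CMA with a substance-specific washout, overall and by calendar year. It is descriptive, expects few patients and has no pre/post comparison, so it mitigates the gap without filling it.
- That the share lost equals Objective 4's non-first share. That share is only a lower bound.
- That the tables should be aligned to the abstract's exposure line. The abstract's own population section and section 7 give any class, so that line is the one out of step.

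Two limits on the impact also stand. The planned Objective 3 comparison is a standardised mean difference of conditions, which works on proportions. And section 11 puts meningioma counts in the hundreds in most databases and says a study of the effect in that population is not feasible, so no cohort choice will make this a decisive test.

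**Conclusion.** The point holds for NOMAC and CMA starts after another study class. Objective 3 as written does not characterise them, so its Table 11 hypothesis and dose counts would be examined in a selected subset whose size can move with the intervention. The omission follows from the text and needs no assumption.

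Its size does. The 14% to 43% range rests on an assumed rise in the share lost from 30% to between 40% and 60%, with constant total initiations; the protocol gives neither share. The intervention-related shift applies mainly to high-dose products, which are the ones moved out of first line, and only where the earlier treatment belongs to a study class. It would be wrong to conclude that any observed fall must be selection: part of it could be, and the planned Objective 3 analysis could not separate the two. The empty rows are a lesser matter of presentation.

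**What to change.** - For NOMAC and for CMA, run the Objective 3 characterisation and the pre/post standardised mean differences in the first-ever user cohorts that Table 4 already defines for Objectives 2, 4 and 5. Report prior meningioma as a proportion of each cohort, beside the count.
- Keep the any-class-naive cohort as the description of all classes, state that scope, and drop its empty look-back rows for the study classes.
- Correct the abstract's Objective 3 exposure line so that it lists both cohorts, and add the NOMAC and CMA cohorts to Objective 3 in Tables 1, 4, 6 and 7.
- Reconcile the Objective 3 code list in Appendix I with Table 7 on G03AC06 and G03DA02. Also reconcile the six classes counted in section 8.4 with the two classes and three progestogens of section 8.6.2.

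The cost is additional tables. No new cohort has to be built for NOMAC or CMA.

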## 8.5 Study population with inclusion and exclusion criteria

The source population will comprise all females aged >10 present in the database at any time during the period from  $1^{st}$  of January 2010 (or start according to the database) to end of data availability. All patients will need to have at least 365 days of data visibility prior to index date.

For patient-level DUS, the study population will be additionally restricted to new medicine users (see "8.6. Variables" for further details). For objective 2, 4 and 5 these will be restricted to participants newly

 $^{2}$  Indicating whether patients are allowed to enter the study population only once or multiple times

<sup>3 IP = inpatient, OP = outpatient

<sup>4 RxNorm codes will be identified based on ATC codes.

P3-	C3-0	206	Study	/ Pro	tocol

Version: V4.0

Dissemination level: Public

prescribed with NOMAC or CMA. For objective 3, these will be all drug classes of interest. A preliminary list of concepts for meningioma can be found in **Appendix I**.

Further information on exposures can be found in see "8.6.1. Exposures". The operational definitions of the inclusion and exclusion criteria are presented by means of **Table 5** and **Table 6**, respectively.

**Table 5.** Operational definitions of inclusion criteria.

Criterion	Details	Order of application 	Assessment window	Care Settings 	Code Type	Diagnosis position 	Applied to study populations:
Observation period during the study period	All individuals present after the study start date	N/A	N/A	IP, OP	N/A	N/A	All
Sex	Females only	N/A	N/A	IP, OP	N/A	N/A	All
Age	Individuals aged >10	Before	N/A	IP, OP	N/A	N/A	All
History of meningioma	Individuals with prior history of meningioma	Before	[-Inf, -1]	IP, OP	SNOME D	Any	Patients with prior history of meningioma (objective 1, subgroup analysis)

<sup>1 Relative to the study entry date

**Table 6.** Operational definitions of exclusion criteria.

Criterion	Details	Order of application	Assessment window	Care Settings 	Code Type	Diagnosis position 	Applied to study populations:
Prior database history	Study participants with less than 365 days of prior history observed at index date will be excluded	Before	[-365, -1]	IP, OP	N/A	N/A	General population (objective 1 and 6)

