Prior database history	Study participants with less than 365 days of prior history observed at index date will be excluded	After	[-365, -1]	IP, OP	N/A	N/A	All except general population (objective 1 and 6)
Prior use of NOMAC	Individuals with prior prescriptions of NOMAC will be excluded	After	[-Inf, -1]	IP, OP	N/A	N/A	New users of NOMAC (objective 2, 4 and 5)
Prior use of CMA	Individuals with prior prescriptions of CMA will be excluded	After	[-Inf, -1]	IP, OP	N/A	N/A	New users of CMA (objective 2, 4 and 5)

<sup>2 IP = inpatient, OP = outpatient

<sup>3 Specify whether a diagnosis code is required to be in the primary position (main reason for encounter)

Authors: [name], [name], [name], [name], [name]

Version: V4.0

**Dissemination level:** Public

Prior use of	Individuals with prior	After	[-Inf, -1]	IP, OP	N/A	N/A	New users of
drug classes	prescriptions of any of the						drug classes
of interest	drug classes of interest will be						or
(any)	excluded						progestogens
							of interest
							(objective 3)

<sup>1 Relative to the study entry date

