#### Objective 1:

Monthly incidence rates with 95% CI will be calculated as the number of new prescriptions per 100,000 person-years of the population at risk during the study period. Each of the drug classes and progestogens of interest will be treated as a separate outcome (see "8.6.2. Outcomes" for more information).

A washout window of 365 days will be applied after each treatment episode. Therefore, participants with an outcome record will not contribute time to the study during the 365 days following the end of each treatment episode. Participants will be able to re-enter the study after the washout window has passed. This washout will be applied for each outcome separately and will be specific to the drug class or progestogen of interest being under study. Please note that a treatment episode might consist of several consecutive prescriptions (see "8.6. Variables" for more information).

Period prevalence with 95% CI will be calculated as the proportion of study participants who were prescribed with an outcome medication monthly.

Objective 1 will only be conducted for complete calendar months observed in the database (e.g., if the end of available data is 15th of June 2023, only data up to 31st May 2023 will be considered). Results will be reported overall and stratified by study period (pre- vs. postintervention), age group (10-17, 18-34, 35-49, 50-64, +65), dose (high- vs. low- dose products, for NOMAC and CMA only), indication (non-HRT vs. HRT) and WHO 5th ATC level codes (if counts allow).

A subgroup analysis will be conducted restricting the study population to those individuals with a prior history of meningioma. All individuals within the study population with a documented history of meningioma will be included, irrespective of the time elapsed since their diagnosis, and will contribute time to the analysis from the date of diagnosis. Given the limited number of feasibility counts for this condition, results will only be reported overall and by calendar years. Please see the limitation section for further details.

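### Tables 4, 5 and 6 define the Objective 1 meningioma-history subgroup in ways that conflict with section 8.8

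*Protocol*

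**What the plan says.** Four places in the protocol define this subgroup.

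- **Section 8.4, Table 4.** Time 0 is the diagnosis, and entry is incident with respect to meningioma: "Date of diagnosis Single entry Incident [-Inf, 0" (the window closes at day 0). The NOMAC new-user row, by contrast, reads "Date of prescription Single entry Incident [-Inf, -1" (closing at day -1). A footnote fixes the entry date for the population-level objectives: "Study entry date (objective 1 and 6) will be defined as the latest of the following: 1) study start date", the tenth birthday, and one year of recorded history. Diagnosis is not among its components.
- **Section 8.5, Table 5.** The inclusion criterion for the subgroup is "Individuals with prior history of meningioma Before [-Inf, -1". The footnote on the order-of-application column says "Relative to the study entry date".
- **Section 8.5, Table 6.** For every population except the general one: "Study participants with less than 365 days of prior history observed at index date will be excluded After [-365, -1".
- **Section 8.8, Objective 1.** "All individuals within the study population with a documented history of meningioma will be included, irrespective of the time elapsed since their diagnosis". Their time counts from the diagnosis date, and results are given only overall and by calendar year.

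**The concern.** This subgroup is the protocol's only population-level view of prescribing to women in whom the products are contraindicated. Section 8.7 already expects it to be small, and section 11 puts meningioma counts in the order of hundreds in most databases.

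Tables 4 to 6 are the operational definitions, and each data partner will run the code locally. A programmer who works from the tables would build a different cohort from one who works from section 8.8. Depending on how the windows are read, the table-based cohort is empty, or it is cut down to women diagnosed before they entered the study. In the second case, women diagnosed during follow-up never appear, including those diagnosed around or after the 2022 measures.

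**Working it through.** The protocol gives no figure to reproduce for this subgroup, so the check is one of logic.

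**Step 1. Table 4.** Day 0 is the diagnosis. A washout over [-Inf, 0] requires no meningioma record up to and including day 0, yet the qualifying record lies on day 0. Read literally as a washout, no woman passes. Every other washout in Table 4 ends at day -1, and so does the meningioma washout in Table 8.

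**Step 2. Table 5.** The window is [-Inf, -1], and its anchor is not stated outright.
- Counted from study entry, it keeps only women with a record before entry.
- Counted from the first diagnosis (the Table 4 anchor), it keeps none, because a first record has no earlier one.

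**Step 3. Table 6.** Index is the diagnosis, so a woman diagnosed with under 365 days of record is excluded. Now take Table 5 from study entry, and a woman whose entry date is set by the one-year-history rule (entry = start of record + 365 days). Table 5 needs diagnosis before that date and Table 6 needs diagnosis no earlier than that date. She cannot meet both.

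**Step 4. Illustration.** The rules were applied to six invented women. Their dates are assumptions, not protocol data. Study start is 1 January 2010.

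| Woman: record start, first diagnosis | Study entry | Table 4, [-Inf, 0] | Table 4 if [-Inf, -1] | Table 5 from entry | Table 5 from diagnosis | Table 6 at diagnosis | Start under 8.8 |
|---|---|---|---|---|---|---|---|
| A: Jan 2005, Jun 2008 | Jan 2010 | no | yes | yes | no | yes | Jan 2010 |
| B: Jan 2005, Jun 2015 | Jan 2010 | no | yes | no | no | yes | Jun 2015 |
| C: as B, code repeated in 2016 | Jan 2010 | no | yes | no | no | yes | Jun 2015 |
| D: Jan 2014, Jun 2014 | Jan 2015 | no | yes | yes | no | no | Jan 2015 |
| E: Jan 2014, Jan 2018 | Jan 2015 | no | yes | no | no | yes | Jan 2018 |
| F: Jun 2009, Sep 2009 | Jun 2010 | no | yes | yes | no | no | Jun 2010 |
| Kept | | 0 of 6 | 6 of 6 | 3 of 6 | 0 of 6 | 4 of 6 | 6 of 6 |

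Table 5 from entry combined with Table 6 keeps only A, 1 of 6. Correcting Table 4 alone brings that table into line with section 8.8, but Tables 5 and 6 still remove women whom section 8.8 includes. The counts show which kinds of women each rule drops. They do not estimate how many.

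**The case against.** The strongest reply is that section 8.8 already settles the rule in words, so the tables are merely badly edited. Much of this stands: the intent is clear, and no redesign is needed. The tables still have to be brought into line, because they are what gets programmed.

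Two readings of the tables soften the conflict.
- [-Inf, 0] could be a look-back for history that includes the diagnosis day. The column heading and the incident entry type speak against this, but it is possible. On that reading Table 4 agrees with section 8.8, while Tables 5 and 6 still do not.
- The Table 5 footnote belongs to the order-of-application column, so counting the assessment window from study entry is an inference. The other available anchor, the first diagnosis, gives a worse result.

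The stakes are also modest. Section 11 calls the subgroup descriptive, and no hypothesis rests on it. Objective 3 reports prior meningioma among new users, and Objective 5 reports meningioma during treatment.

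A reader might infer two stronger claims, and the documents support neither.
- *The subgroup will be empty.* This follows from Table 4 only if the cell is read as a washout, and from Table 5 only if its window runs from first diagnosis.
- *Most eligible women will be lost.* A share can be computed only by treating open databases as closed cohorts with a constant diagnosis rate. For NAJS, with data from 2017 and a lock in November 2023, that means 1 year before entry and about 5.9 after. The share of women kept is then 1/(1 + 5.9) = 14.5%. The share of person-time kept is 1/(1 + 5.9/2) = 25.3%, since women diagnosed during follow-up contribute about half of it. The answer moves with the unit chosen, ignores women who join later, and leaves out Table 6. It is not a finding about this protocol.

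**Conclusion.** Wrong as written. Tables 4, 5 and 6 do not implement the subgroup that section 8.8 describes, and no reading of them makes all four places agree. The Table 4 problem depends on taking the cell as the washout that its column heading names. The Table 5 problem arises under either anchor. The Table 6 problem depends on index being the diagnosis date, as Table 4 sets it.

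The size of the loss cannot be derived from the protocol. The consequence is confined to one descriptive subgroup analysis and does not touch the main Objective 1 results or the interrupted time series. It deserves correction before coding because the subgroup is small and the correction is cheap.

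**What to change.** 1. Table 4, subgroup row: set the washout to [-Inf, -1], so that entry is the first recorded diagnosis.
2. Table 5, history of meningioma: define history as a meningioma record on or before each day of follow-up, so that entry is time-varying.
3. Table 6: for this subgroup, assess the 365-day requirement at study entry instead of at diagnosis. The study entry date already includes one year of recorded history, so this brings in no one whom the general population excludes.
4. Section 8.8: state that person-time starts at the later of study entry and date of diagnosis.

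Under these rules all six women in the illustration enter, on the dates in the last column. The cost is a few table cells and one sentence. No new data are needed.
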